13.1.4.2 Primary Analysis

An analysis of covariance model with treatment group as factor and baseline HAM-A as covariate will be used to test the null hypothesis that there is no difference between PH94B- and placebo-treated subjects in change from baseline to end of treatment in HAM-A scores. (SAS PROC MIXED, version 9.4).

13.1.4.3 Secondary Analyses

CGI-I and PGI-C at end of treatment will be analyzed using a normal approximation test for the difference between 2 binomial proportions. The null hypothesis to be tested is that there is no difference between PH94B- and placebo-treated subjects. (SAS PROC FREQ, version 9.4).

Change from baseline to Week 4 in ADNM total score will be analyzed analogously to the primary endpoint.

Change from baseline to Week 4 in IADQ total score will be analyzed analogously to the primary endpoint.

[REDACTED]

[REDACTED]

[REDACTED]

[REDACTED]

[REDACTED]

13.1.5 Safety and Tolerability Analyses

Safety in this study will be determined from evaluation of AEs, clinical laboratory assessments, vital signs assessments, physical examinations including examination of the nasal passages, and ECGs. Specific visits for obtaining clinical laboratory assessment samples are listed in the schedule of events (Table 2-1). Details of clinical laboratory tests are provided in Section 10.3.2.1.1.

Descriptive statistics will be used to summarize safety and tolerability of PH94B (3.2 μ g) as measured by reports of AEs and SAEs, changes in clinical laboratory values, ECGs, vital signs, and physical examinations, as well as suicidal ideation (as documented using the C-SSRS and MADRS scores), and withdrawal effects (PWC-20).

Safety analyses will be conducted using data from the safety population (as defined in Section 13.1.1).

13.1.5.1 Adverse Events

All AEs will be coded using the most recent version of Medical Dictionary for Regulatory Activities.

Treatment-emergent AEs are defined as:

- AEs with onset at the time of or following the start of treatment with IP through the Follow-up Visit or
- AEs starting prior to the start of treatment but increasing in severity or relationship at the time of, or following, the start of treatment with IP through the Follow-up Visit

Adverse events will be classified by time of occurrence group assignment to more clearly identify those arising after exposure to placebo only and those arising after exposure to PH94B.

The number and percentage of subjects with AEs will be displayed for each treatment group by system organ class and preferred term. Summaries of AEs by severity and relationship to IP will also be provided. Serious AEs and AEs resulting in discontinuation of IP will be summarized separately in a similar manner. Subject listings of AEs, SAEs, and AEs causing discontinuation of IP will be produced.

13.1.5.2 Clinical Laboratory Evaluations

Descriptive summaries (mean, SD, median, minimum, and maximum) of actual (absolute) values and changes from baseline values will be presented for clinical laboratory values for each treatment group at each time point.

The number of subjects with clinical laboratory values categorized as below, within, or above normal ranges will be tabulated showing change from baseline (shift tables) for each clinical laboratory analyte by treatment group and by study visit.

Laboratory values that are outside the normal range will also be flagged in the data listings and presented with the corresponding normal ranges. Any out-of-range values that are identified by the Investigator as being clinically significant will also be shown in a data listing.

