13.1.5.3 Vital Signs

Descriptive summaries (mean, SD, median, minimum, and maximum) of actual values and changes from baseline will be calculated for systolic blood pressure, diastolic blood pressure, heart rate, and respiratory rate.

The number of subjects with vital signs values categorized as below, within, or above normal ranges will be tabulated showing change from baseline (shift tables) for each parameter by treatment group and by study visit. Pre- and post-treatment values may also be presented with an analysis of mean changes from baseline.

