13.1.5.5 Physical Examination Findings

The number and percentage of subjects with normal and abnormal findings in the complete physical examination, including nasal passages examination, will be displayed for each treatment group.

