9.2. Clinical Laboratory Evaluations

Descriptive summaries of observed values and change from baseline values will be presented for continuous hematology, chemistry (also including prolactin and thyroid function parameters) for each treatment group and overall subjects at each study visit. Urinalysis results will be listed.

Laboratory values that are outside the normal range will also be flagged in the data listings and presented with the corresponding normal ranges. Any out-of-range hematology or clinical chemistry values that are identified by the investigator as being clinically significant will also be shown in a separate data listing.

Urine drug screen and pregnancy test results will be listed.

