9.3. Vital Signs

Descriptive summaries of observed values and changes from baseline will be calculated for systolic blood pressure (mmHg), diastolic blood pressure (mmHg), heart rate (beats/min), respiratory rate (breaths/min), and temperature (°C), overall, by treatment group, and by study visit.

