10.1. Coronavirus 2019 (COVID-19) Impact

The SARS-CoV-2 virus and variants may still be a threat and safety precautions may still be in place during study enrollment. To assess the impact of the COVID-19 pandemic on study procedures, study staff will complete the COVID-19 Impact questionnaire. Should a study visit be affected by COVID-19, study staff will record how the visit was affected (missed, abbreviated, delayed, performed remotely, or otherwise deviating from the planned format in the protocol) and which procedures were impacted. All COVID-19 protocol deviations will be provided in a separate listing. This listing will include the subjects, affected visits, and affected assessments.

11. Changes from Planned Analysis

Study staff will complete the Coronavirus 2019 (COVID-19) Impact questionnaire to assess the impact of the COVID-19 pandemic on study procedures. The COVID-19 Impact questionnaire is described in Section 10.1. All COVID-19 protocol deviations will be provided in a separate listing.

The ADNMs subscales exploratory endpoints analysis will not be completed as part of this SAP.

Physical examination and urinalysis results will not be summarized using descriptive statistics but will be listed.

The treatment failure sensitivity analysis will be replaced with a control-case sensitivity analysis that imputes the mean change from baseline to Week 6 in HAM-A total scores from the placebo group for missing change from baseline responses. This approach accounts for the potential for a

high placebo response.

12. References

- ASA. (2018) Ethical Guidelines for Statistical Practice. Prepared by the Committee on Professional Ethics, April 2018. <http://www.amstat.org/about/ethicalguidelines.cfm>
- Carpenter JR and Kenward MG. *Multiple Imputation and its Application (Statistics in Practice)*. Chichester, West Sussex, UK: John Wiley & Sons; 2013.
- Graham JW, and Olchowski AE, Gilreath TD. (2007) “How Many Imputations are Really Needed? Some Practical Clarifications of Multiple Imputation Theory.” *Prev Sci.* 2007;8(3): 206-213.
- ICH (1998). ICH Harmonised Tripartite Guideline. Statistical Principles for Clinical Trials E9; 1998. https://database.ich.org/sites/default/files/E9_Guideline.pdf
- Little R and Rubin D. (1987). *Statistical Analysis with Missing Data*, New York: Wiley.
- RSS. (2014) *The Royal Statistical Society: Code of Conduct*, 2014. <https://rss.org.uk/about/policy-and-guidelines/code-of-conduct/>.

13. Tables and Listings

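### The SAP drops the protocol's laboratory and vital-sign shift tables without declaring it and, by a declared change, lists nasal findings, so no table counts new out-of-range values or abnormal nasal findings by arm

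*Protocol*

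**What the plan says.** Protocol 13.1.5.2 promises two displays for laboratory data. One is a descriptive summary. The other is a count of subjects with low, normal or high values, which "will be tabulated showing change from baseline (shift tables) for each clinical laboratory analyte by treatment group and by study visit". Protocol 13.1.5.3 makes the same promise for vital signs: counts "will be tabulated showing change from baseline (shift tables) for each parameter by treatment group and by study visit". Protocol 13.1.5.5 adds, for physical findings: "The number and percentage of subjects with normal and abnormal findings in the complete physical examination, including nasal passages examination, will be displayed" by treatment group.

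SAP 9.2 keeps the first laboratory display: "Descriptive summaries of observed values and change from baseline values will be presented for continuous hematology, chemistry" and related parameters. It then sends out-of-range values to flagged listings. SAP 9.3 gives only descriptive summaries of vital signs. SAP 9.5 lists physical findings with abnormal results flagged.

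SAP Section 11, which records departures from the protocol, states: "Physical examination and urinalysis results will not be summarized using descriptive statistics but will be listed". It says nothing about shift tables.

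**The concern.** Changes in laboratory values, vital signs and physical findings are named safety endpoints in both documents, and safety is the secondary objective. A protocol-specified comparison has gone from the SAP with no reason given, although Section 11 records other changes to the safety outputs. A reader of the study report could not tell whether the omission was a decision or an oversight.

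The nasal findings matter because of the route. Protocol 5.3 names local nasal reactions as a possible risk. The nasal passages are examined at Visits 1, 3, 4, 5 and 6. The synopsis describes earlier exposure as under 2 weeks at fewer than 4 doses a day, whereas this trial gives 4 doses a day for 4 weeks. There is no data safety monitoring board and no interim analysis, so the end-of-study tables are the main aggregate view of safety.

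**Working it through.** The plan states no figure on this point, so the check is mainly a comparison of texts.

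| Output | Protocol | SAP text | SAP index and shells | Declared in SAP 11? |
|---|---|---|---|---|
| Hematology and chemistry shifts | 13.1.5.2: by analyte, arm, visit | 9.2: descriptive summaries only | Tables 14.3.5.1 and 14.3.5.2: n, mean (SD), median, min, max | No |
| Vital-sign shifts | 13.1.5.3: by parameter, arm, visit | 9.3: descriptive summaries only | Table 14.3.6.1, same shell | No |
| Physical and nasal findings, n (%) | 13.1.5.5: by arm | 9.5: listed | Listing 16.2.9.3 only | Yes, as physical examination; the nose is not named |
| ECG normal/abnormal counts | 13.1.5.4 | 9.4: kept | Tables 14.3.6.2.1 and 14.3.6.2.3 | Not needed |

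Urinalysis is also a declared listing, so the undeclared laboratory gap is hematology and chemistry, including prolactin and thyroid tests. The ECG row shows that the SAP keeps by-arm abnormality counts elsewhere.

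**What remains visible**
- The shared shell prints minimum and maximum for both the value and its change, by arm and visit.
- Tables 14.3.4.1 and 14.3.4.2 show, subject by subject, the hematology and chemistry abnormalities judged clinically significant.
- Laboratory and vital-sign listings carry range flags; the examination listing flags abnormal results.
- Protocol 10.3.2.1.3 and 11.2.1 turn clinically relevant laboratory changes and visit observations into adverse events, which are tabulated by arm.

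None of these counts, by arm, the subjects who moved from normal to out of range.

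**How far a table of means would show such subjects (assumed values)**

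Inputs: 40 subjects randomized 1:1 (synopsis), so n = 20 per arm. The SD is taken as 1 in each arm. The number of subjects who shift, k, and the rise, r, are assumptions.

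- Shift in arm mean = k × r / n.
- Standard error of the difference between arms = √(2/n) = √(2/20) = 0.316 SD.

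| k | r (SD) | Mean shift (SD) | Ratio to standard error |
|---|---|---|---|
| 1 | 2 | 1 × 2/20 = 0.10 | 0.32 |
| 1 | 3 | 1 × 3/20 = 0.15 | 0.47 |
| 2 | 3 | 2 × 3/20 = 0.30 | 0.95 |
| 3 | 2 | 3 × 2/20 = 0.30 | 0.95 |
| 3 | 3 | 3 × 3/20 = 0.45 | 1.42 |

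Across this range the means would not clearly separate the arms. The maximum row would show the most extreme value, but not whether one subject or three lay near it. A shift table would show 1 of 20 (5%) to 3 of 20 (15%).

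**The case against.** A reader might infer that the safety tables hide individual abnormalities. They do not. Suppose one subject of 20 rose from 0.6 to 5 times the upper limit, the others staying at 0.6. The arm mean would move by (5 − 0.6)/20 = 0.22, from 0.60 to 0.82, and would still look normal. But the same table would print a maximum of 5.0 and a maximum change of 5 − 0.6 = 4.4. A value that large would also probably be judged clinically significant, and so reach Table 14.3.4.2 and the adverse event tables. The real gap is the milder shift not judged significant.

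A reader might also infer that the nose gets no comparison between arms, or that this change was made silently. Neither follows. Clinically relevant nasal observations are adverse events under Protocol 11.2.1 and are tabulated by arm, and Section 11 openly moves the physical examination to a listing.

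It is also fair to say that this is a 40-subject exploratory study with descriptive safety analysis, and that listings sorted by treatment can be read by hand. Vital-sign shifts also need normal ranges, which neither document gives; Listing 16.2.9.1 only has a column for them.

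All of this stands, and it limits the consequence. It does not explain why specified tables are absent without a declaration. Nor does it supply the counts: the displays of significant values rest on investigator judgement and cover only hematology and chemistry.

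**Conclusion.** The mismatch is real. The laboratory and vital-sign shift tables are missing from the SAP text, index and shells, and Section 11 does not declare it. The move of physical and nasal findings to a listing is declared, but it still departs from Protocol 13.1.5.5.

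The loss is of counts and not of sight of individual extremes. No table compares by arm the number of subjects with new out-of-range laboratory or vital-sign values, or with abnormal nasal findings that were not reported as adverse events. No efficacy estimate or test changes.

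The conclusion assumes that the SAP's index and shells are the full set of planned outputs. The 0.10 to 0.45 SD range rests on assumed shifts and 20 subjects per arm; the textual finding does not depend on it.

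**What to change.** Before unblinding:
- In SAP 9.2 and Table 7, restore Baseline-to-Visit 6 low/normal/high shift tables for hematology and for chemistry, by arm.
- In SAP 9.3 and Table 7, restore vital-sign shift tables by arm at Visits 3 to 7, and state the normal ranges used.
- Add one n (%) table of normal and abnormal nasal findings by visit and arm, and amend the Section 11 entry to match.

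If the sponsor prefers not to restore the shift tables, the minimum is an entry in Section 11 recording the omission and its reason.

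The cost is about four standard tables and no new data collection. Laboratory and vital-sign range flags already appear in the listing shells, and nasal results are recorded as normal or abnormal at each examination. The only new content is the set of vital-sign ranges.

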13.1.5.3 Vital Signs

Descriptive summaries (mean, SD, median, minimum, and maximum) of actual values and changes from baseline will be calculated for systolic blood pressure, diastolic blood pressure, heart rate, and respiratory rate.

The number of subjects with vital signs values categorized as below, within, or above normal ranges will be tabulated showing change from baseline (shift tables) for each parameter by treatment group and by study visit. Pre- and post-treatment values may also be presented with an analysis of mean changes from baseline.

13.1.5.4 Twelve-lead Electrocardiograms

The number and percentage of subjects with normal and abnormal ECG findings will be summarized for each treatment group at each time point. Abnormal results will be grouped as clinically significant and not clinically significant.

A comparison of QT results will be presented. Summary statistics for baseline values at Screening (Visit 1) and Follow-up will be displayed by treatment group for QT and the QT interval corrected for heart rate (QTc). In addition, the number and percent of subjects in each treatment group who experienced a change >30 ms or a change >60 ms will be presented.

Descriptive summaries (mean, SD, median, minimum, and maximum) will be presented for ECG measures of PR interval, QRS interval, QT interval, QTc interval (both correction methods), and heart rate for each treatment group at each time point.

[figure not shown]
13.1.5.5 Physical Examination Findings

The number and percentage of subjects with normal and abnormal findings in the complete physical examination, including nasal passages examination, will be displayed for each treatment group.

13.1.6 Interim Analysis

No interim analyses are planned.

13.2. [REDACTED]

14. STUDY CONDUCT

Steps to ensure the accuracy and reliability of data include the selection of qualified investigators and appropriate study sites, review of protocol procedures with the Investigator and associated personnel before the study, periodic monitoring visits, and meticulous data management.

14.1. Sponsor and Investigator Responsibilities

14.1.1 Sponsor Responsibilities

The sponsor is obligated to conduct the study in accordance with strict ethical principles (Section 16). The sponsor reserves the right to withdraw a subject from the study (Section 8.3), to terminate participation of a study site at any time (Section 14.7), and/or to discontinue the study (Section 14.6).

VistaGen Therapeutics, Inc. agrees to provide the Investigator with sufficient material and support to permit the Investigator to conduct the study according to the study protocol.

14.1.2 Investigator Responsibilities

By signing the Investigator's Agreement (Section 18.1), the Investigator indicates that he or she has read the protocol carefully, fully understands the requirements, and agrees to conduct the study in accordance with the procedures and requirements described in this protocol.

The study will be conducted in accordance with ICH GCP and applicable United States Code of Federal Regulations (CFR). The Principal Investigator will assure that no deviation from, or changes to, the protocol will take place without prior agreement from the Investigational New Drug (IND) sponsor, funding agency and documented approval from the IRB, except where necessary to eliminate an immediate hazard(s) to the study subjects. All personnel involved in the conduct of this study have completed Human Subjects Protection and ICH GCP training.

Investigators should ensure that all persons who are delegated study-related responsibilities are adequately qualified and informed about the protocol, the IP(s), and their specific duties within the context of the study. Investigators are responsible for providing VistaGen Therapeutics, Inc. with documentation of the qualifications, GCP training, and research experience for themselves and their staff as required by the sponsor and the relevant governing authorities.

To ensure compliance with the guidelines, the study may be audited by an independent person. The Investigator agrees, by written consent to this protocol, to cooperate fully with compliance checks by allowing access to all study documentation by authorized individuals.

14.1.3 Confidentiality and Privacy

Subject confidentiality and privacy are strictly held in trust by the participating investigators, their staff, and the sponsor and their staff. This confidentiality is extended to cover testing of biological samples and genetic tests in addition to the clinical information relating to subjects. Therefore, the study protocol, documentation, data, and all other information generated will be held in strict confidence. No information concerning the study or the data will be released to any unauthorized third party without prior written approval of the sponsor.

All research activities will be conducted in as private a setting as possible.

The study monitor, other authorized representatives of the sponsor, representatives of the IRB, regulatory agencies, or pharmaceutical company supplying study product may inspect all

documents and records required to be maintained by the Investigator, including, but not limited to, medical records (office, clinic, or hospital) and pharmacy records for the subjects in this study. The clinical study site will permit access to such records.

The study subject's contact information will be securely stored at each clinical site for internal use during the study. At the end of the study, all records will continue to be kept in a secure location for as long a period as dictated by the reviewing IRB, institutional policies, or sponsor requirements.

Study subject research data, which is for purposes of statistical analysis and scientific reporting, will be transmitted to and stored at Premier Research. This will not include the subject's contact or identifying information. Rather, individual subjects and their research data will be identified by a unique study identification number. The study data entry and study management systems used by clinical sites and by Premier Research staff will be secured and password protected. At the end of the study, all study databases will be de-identified and archived at Premier Research.

14.2. Site Initiation

Study personnel may not screen or enroll subjects into the study until after receiving notification from the sponsor or its designee that the study can be initiated at the study site. The study site will not be authorized for study initiation until:

1. The study site has received the appropriate IRB approval for the protocol and the appropriate ICF.
2. All regulatory documents have been submitted to and approved by the sponsor or its designee.
3. The study site has a Clinical Trial Agreement in place.
4. Study site personnel, including the Investigator, have participated in a study initiation meeting.

14.3. Screen Failures

Subjects who fail inclusion and/or exclusion criteria may not be rescreened for the study.

Screen failures are defined as subjects who consent to participate in the clinical study but are not subsequently entered in the study. A minimal set of screen failure information is required to ensure transparent reporting of screen failure subjects to meet the Consolidated Standards of Reporting Trials publishing requirements and to respond to queries from regulatory authorities. Minimal information includes demography, screen failure details, eligibility criteria, and any SAE.

14.4. Study Documents

All documentation and material provided by VistaGen Therapeutics, Inc. for this study are to be retained in a secure location and treated as confidential material.

14.4.1 Informed Consent

Informed consent forms describing in detail the study intervention, study procedures, and risks are given to the subject and written documentation of informed consent is required prior to starting intervention/administering study intervention.

Informed consent is a process that is initiated prior to the individual's agreeing to participate in the study and continues throughout the individual's study participation. Consent forms will be IRB approved and the subject will be asked to read and review the document. The Investigator will explain the research study to the subject and answer any questions that may arise. A verbal explanation will be provided in terms suited to the subject's comprehension of the purposes, procedures, and potential risks of the study and of their rights as research subjects. Subjects will have the opportunity to carefully review the written ICF and ask questions prior to signing. The subject should have the opportunity to discuss the study with their family or surrogates or think about it prior to agreeing to participate. The subject will sign the informed consent document prior to any procedures being done specifically for the study. Subjects must be informed that participation is voluntary and that they may withdraw from the study at any time, without prejudice. A copy of the ICF will be given to the subjects for their records. The informed consent process will be conducted and documented in the source document (including the date) and the ICF signed before the subject undergoes any study-specific procedures. The rights and welfare of the subjects will be protected by emphasizing to them that the quality of their medical care will not be adversely affected if they decline to participate in this study.

